IDWG	Inter-Dialytic Weight Gain
IL	Interleukin
IRB	Institutional Review Board
LE	Leukocytes
LVEF	Left Ventricular Ejection Fraction
M ϕ	Marcophage
MO	Monocyte
MOD	Multi-Organ Dysfunction
MS	Myocardial Stunning
NE	Neutrophils
NIH	National Institute of Health
PMN	Polymorphonuclear
RCA	Regional Citrate Anti-Coagulation
RR	Respiratory Rate
SAE	Serious Adverse Event
SCD	Selective Cytopheretic Device
SHH	Standard Heparin Hemodialysis
T2D	Type II Diabetes
TNF- α	Tumor Necrosis Factor-alpha
UF	Ultrafiltration
WBC	White Blood Cell Count

Study Synopsis

Study Objectives	
 ❖ To diminish the ischemia induced myocardial stunning events observed in ERSD patients on chronic hemodialysis requiring aggressive ultrafiltration
Study Design	
 ❖ This is a Phase II trial. ❖ Myocardial stunning events and biomarker measurements will be compared pre and post hemodialysis with standard heparin anticoagulated hemodialysis treatment and after one hemodialysis treatment with the regional citrate anticoagulated SCD device.
Study Population	
 ❖ The subject population to be studied are those who have been on chronic hemodialysis for \geq 3 months ❖ It is estimated that up to 10 Subjects will be studied in this protocol.
Entry Criteria	
 ❖ Inclusion Criteria 
 1. End-stage renal disease (CKD Stage 5) 2. Receiving chronic hemodialysis thrice weekly for \geq 3 months 3. Current dialysis access is a well-functioning arteriovenous (AV) graft, AV fistula, or cuffed tunneled catheter 4. Patient can safely receive chronic hemodialysis thrice weekly with heparin anticoagulation 5. Patient has achieved $Kt/V \geq 1.2$ over the preceding 2 months 6. Patient has no contraindication for regional citrate anticoagulation 7. Baseline blood pressure before hemodialysis has been $\geq 100/50$ over preceding 4 weeks 8. Able to and have given informed consent 9. Recurrent intradialytic weight gain >0.04 kg/kg body weight at the beginning of the week (i.e. Monday or Tuesday). Recurrent is defined as at least two of eight sessions the past 60 days or at least three of twelve sessions the past 90 days. 
OR
 
Intradialytic hypotension (IDH) prone (IDH greater than 30% of dialysis sessions in month before session) IDH defined as systolic blood pressure (SBP) less than 100 mmHg or SBP decrease greater than $>10\%$ of predialysis with symptoms
 
 10. Age ≥ 18 years ❖ Exclusion criteria:

	
 1. Severe heart failure (NY Heart Association functional class greater than or equal to 3) 2. Cardiac transplant recipient 3. Mental incapacity to consent 4. Human immunodeficiency virus (HIV) 1 or 2 Ab (+) 5. Any active inflammatory condition (e.g., gout, systemic lupus erythematosus flare, hepatitis B or C infection, allograft rejection, subcutaneous injection of illicit drugs, “skin popping”) 6. Treatment with immunosuppressive therapy (e.g anti-neoplastic agents, glucocorticoids, calcineurin inhibitors) within 30 days of the treatment program 7. Hemoglobin (HgB) <9 g/dL 8. Platelet count <50,000/mm³ 9. WBC <4,000/mm³ 10. Acute coronary syndrome, including myocardial infarction within 90 days of the treatment period 11. Ischemic cardiomyopathy 12. Participation in an experimental drug or device study, within 30 days of the treatment period 13. Woman who is pregnant, breast feeding a child, or try to become pregnant 14. Inability to comply with Study Procedures 15. Exposure to hemodialysis for less than 90 days 16. Positive test for active infection with COVID-19 virus
Treatment Plan	Each Subject will receive one standard study hemodialysis treatment with heparin anticoagulation during which all procedures noted in Appendix 1 will be performed. Subsequently each subject will receive hemodialysis with the added SCD filter anticoagulated with regional citrate.
Data Safety Monitoring	This is a small feasibility study. A safety analysis will be performed on each patient prior to their next hemodialysis treatment by the PI.
Key Measurements	
 ❖ Adverse events ❖ Regional wall abnormalities and myocardial strain on Echocardiogram
Exploratory Measurements	
 ❖ Soluble Markers (Elastase, Hs CRP, IL-6, IL-10, IL-17, IL-23, G-CSF, TNF-α, MCP-1, L-selectin, neopterin, IL-1β, IL-8) ❖ Leukocyte flow cytometry (circulatory monocyte subsets and circulatory activated neutrophils) ❖ WBC and platelet counts

Primary Analyses	Descriptive analysis will be conducted on the following parameters in all Subjects exposed to any study hemodialysis treatment: 
 ❖ Adverse events ❖ Regional wall abnormalities and myocardial strain ❖ Clinical laboratory and physiological measurements
Secondary Analyses	A number of secondary analyses will be conducted, including the following: 
 ❖ Mean change from baseline in cytokines at the end of each treatment ❖ Mean change from baseline in markers of inflammation at the end each treatment
Study Periods and Study Duration	
 ❖ The total duration of participation will be approximately 3 weeks.

1. Background and Rationale

More than 400,000 people are currently treated by hemodialysis (HD) in the US end stage renal disease (ESRD) program. The mortality in this group of patients is unacceptably high with almost half of the deaths due to cardiovascular disease (CVD). Strategies to reduce the mortality of HD patients with directed interventions at cardiovascular risk factors have largely been ineffective. It is well recognized that HD patients suffer excess morbidity and mortality, mainly due to cardiac failure and sudden death rather than traditional thrombotic occlusion leading to acute myocardial infarction (AMI).^{1,2} The excess cardiovascular risk is not the result of the traditional factors associated with CVD but a combination of non-traditional factors unique to chronic kidney disease (CKD).

There is a growing body of evidence to suggest that a combination of multiple hemodynamic and inflammatory factors contribute to this elevated risk. These factors operate simultaneously and sequentially, contributing to the poor outcomes. They include the repetitive hemodynamic insult precipitated by rapid volume removal with HD and the immune dysregulation accentuated by dialysis. It has been shown that dialysis is associated with a repetitive ischemic injury termed myocardial stunning (MS)³. A subsequent observational study over 12 months has shown that MS is associated with 30% mortality and 10% reduction in left ventricular ejection fraction⁴. Larger inter-dialytic weight gain (IDWG) with the requirement for larger ultrafiltration volume is strongly associated with MS and increased mortality⁴⁻⁶, specifically for ultrafiltration (UF) requirements exceeding 12.37 ml/h/kg. It seems that HD itself may contribute to the development of heart failure and the risk of sudden death. In addition to the hemodynamic instability precipitated by HD, these patients are subject to substantive metabolic and inflammatory stress⁷.

Since treatment of traditional risk factors for CVD have been ineffective, focus on non-traditional risk factors, especially acute and chronic inflammation, has become a focus of therapeutic interventions in dialysis patients. In this regard, inflammation and its cellular immunologic effector, the activated monocytes (MO), are central to the accelerated progression of CVD in patients with CKD and patients with ESRD on HD. Consequently, a focus on non-traditional and non-modifiable risk factors has emerged with MO activation as a prime therapeutic target. A pivotal pathobiologic role of MO and macrophages (Mφ) on development and progression of atherosclerosis has been clearly established⁸⁻¹⁰. In this regard, heterogeneous subpopulations of MO have been identified in humans. Cell surface expression of CD14 and CD16 identifies 3 functionally distinct subsets of MO: classical (CD14^{hi}, CD16⁻, pro-inflammatory), intermediate (CD14^{hi}, CD16⁺, pro-inflammatory) and non-classical (CD14^{low}, CD16⁺⁺, anti-inflammatory/reparative). Intermediate MO play an instrumental role in the development of atherosclerosis in the general and CKD populations¹¹⁻¹⁴. This subset of M has a greater degree of pro-inflammatory phenotype compared to the other subsets. Furthermore, epidemiologic studies have reported that the number of intermediate MO increases with worsening renal function and higher cell numbers predict adverse cardiovascular outcomes in ESRD patients undergoing chronic dialysis¹⁴⁻¹⁷. This proposal plans to evaluate a novel immuno-modulatory device, the selective cytopheretic device (SCD), on the immune dysregulated state of ESRD and to assess the benefit of this innovative strategy to improve cardiac performance and reduce progressive congestive heart failure (CHF).

The SCD has shown to improve clinical outcomes of critically ill patients with multiorgan dysfunction (MOD) by mitigating the inflammatory cascade. Benefit has also

been indicated with chronic inflammation, such as that observed in end stage renal disease (ESRD). This technology has proven to be effective in pre-clinical animal models of disease for which inflammation is present, such as cardiopulmonary bypass (CPB), septic shock and stroke. This proposal plans to further evaluate therapeutic impact of a novel device (SCD) specifically toward ischemic cardiac events during hemodialysis (HD) in ESRD patients.

SCD Mechanism of Action

The SCD is an immuno-regulating, extracorporeal fiber membrane device targeted to modulate the cardiac ischemic events occurring during HD. The platform of SCD technology is the ability of polysulfone fibers to selectively sequester activated systemic leukocytes (LE), primarily neutrophils (NE) and MO, as they flow through the fiber casing via an extracorporeal circuit. The bound LE are deactivated via exposure to a pharmacologic agent (citrate), resulting in lower ionized calcium (iCa) which resets the excessive/dysregulated activation kinetics of LE to a more normal state, while also providing regional anticoagulation. The reset LE are then released back to the systemic blood. The SCD has demonstrated to ameliorate acute MOD in four clinical trials resulting in a relative 50% reduction in mortality rates of ICU patients with MOD¹⁸⁻²⁰, as well as shifting the circulating MO pool to a less inflammatory phenotype in ESRD patients on chronic HD. The SCD has the potential to transform the therapeutic approach to a disorder that results in progressive cardiac failure in the ESRD population on chronic HD²¹.

Preliminary Clinical Observations

Acute Renal Failure

This approach has been initially evaluated in ICU patients with acute kidney injury (AKI) and multiorgan failure requiring CRRT. These trials were initiated after preclinical experiments in a porcine model demonstrated that SCD therapy had a significant ameliorative effect on sepsis induced organ dysfunction, including cardiac, pulmonary and renal parameters along with an immunomodulatory effect on circulating LE. The clinical evaluation of SCD therapy has been completed in 3 exploratory clinical trials in ICU adult patients with AKI requiring continuous renal replacement therapy (CRRT) and multi organ dysfunction (MOD). These trials have demonstrated an excellent safety profile and suggested efficacy impact. Leukopenia and sustained thrombocytopenia were not observed; accelerated renal recovery with RRT discontinuation and an approximately 15-20 percent or greater improvement in survival rates has been observed compared to conventional RRT. This device is added in series to the CRRT after the standard HD filter. Of note, in all 3 trials SCD therapy was well tolerated, without significant effects on hematological parameters, including white blood counts (WBC) and platelet counts, and with no unanticipated serious adverse events related to SCD therapy. Due to these favorable results in 3 trials, a Phase III controlled, randomized, multicenter clinical trial was undertaken. The control group received standard CRRT with RCA and the SCD treated group received up to 7 days of device therapy. An analysis of per protocol patients demonstrated

no device related serious adverse events. The SCD therapy group had a 60-day mortality rate of 16% compared to 41% in control. The SCD therapy group had no patients with dialysis dependency at day 60 compared to 23% of control patients. The composite end point of either death or dialysis dependency at day 60 was 16% for SCD therapy vs. 58% for control (p=0.01).

Acute Heart Failure and CHF

Over the past decade, a number of novel pharmacologic approaches have failed to prove clinical efficacy, accentuating the need to discover new, safe approaches to treat CHF. Inflammation is central to the development of a variety of acute organ failures, including heart, kidney, lung and brain, as well as chronic organ dysfunction, including heart, kidney and Type 2 Diabetes. CHF and acute decompensated heart failure have been increasingly recognized as associated with chronic systemic inflammation ²². MO and tissue Mφ have been identified as critical sources of systemic inflammation in CHF ²³ and cause a decrease in cardiac myocyte contractility ²⁴. In this regard, the SCD has been assessed in a preclinical model of CHF. SCD efficacy to dampen the cardio-depressant effects associated with the chronic pro-inflammatory state of CHF was evaluated in a preclinical canine CHF model ²⁵ developed and fully characterized by [name]. This model manifests many of the sequelae of CHF in humans, including profound systolic dysfunction, increased systemic vascular resistance and decreased cardiac output ²⁶. It has been used to predict efficacy of new therapies for treatment of CHF ²⁶⁻²⁸. Five dogs with advanced CHF were used in the study set. The effect of SCD therapy on LVEF in this model, demonstrates that this therapy converts viable but non-contracting myocardium to contracting myocardium. The renal effects were also substantive with doubling of urine sodium excretion with SCD therapy compared to baseline. With respect to safety profile, no episodes of arrhythmias or hypotension were observed during the treatment period. Recent ongoing studies supported with NIH funding in this model has demonstrated that this SCD related improved myocardial performance lasts up to 4 weeks after treatment.

Ischemia/Reperfusion Injury of Myocardium

Inflammation with LE infiltration into injured myocardium ²⁹ plays a critical role in the degree of myocardial ischemia reperfusion injury after AMI. To evaluate the ability of SCD therapy to reduce infarct size of AMI, dogs underwent complete occlusion of the circumflex coronary artery with a balloon catheter for 3h followed by 2h of reperfusion after balloon deflation. Control IRI dogs (n=4) received no treatment; SCD therapy was initiated 20-30 minutes prior to reperfusion and continued for the entire 2h reperfusion period (n=3). As demonstrated in Figure 3, SCD therapy had a substantial effect to reduce infarct size reducing the percent of infarct area to total LV mass from control of 19 ± 1.35 to 10.2 ± 2.6 % (p<0.05) in SCD therapy animals. The degree of NE infiltration was markedly diminished in the area of injury. Serum troponin levels were 10x lower in SCD animals compared to controls (data not shown).

Pilot Feasibility Trial of SCD Therapy in ESRD Patients

A pilot safety trial was undertaken by [name] et al. to evaluate SCD therapy in a more stable renal failure patient population. Fifteen ESRD patients with CRP levels above

5mg/L were enrolled to assess the safety and early efficacy signals on inflammatory biomarkers in these patients. After a Non-Significant Risk designation by the Henry Ford Health System (HFHS) IRB, this study was performed ²¹. The clinical results demonstrated an excellent safety profile with no decline in total WBC, NE or platelet counts. To evaluate the effect of SCD therapy on M phenotypes in these patients, determination of CD14^{hi} fluorescent intensity on peripheral blood M was analyzed utilizing flow cytometry. SCD therapy promoted a shift in MO phenotype from predominantly CD14^{hi} expressing MO at baseline/pre-SCD therapy to CD14^{low} expressing MO post-SCD therapy (Figure 4, A/B). In the 13 ESRD patients evaluated, a significant shift in MO population phenotype afforded by a single SCD therapy session was observed ($p<0.013$). In a subset of patients ($n=7$) presenting with T2D, indicative of an even greater chronic inflammatory state, this persistent decline in M CD14 expression was sustained as long as 2 weeks post therapy (Figure 4, C). The average number of cells bound to the SCD membrane following 4 hours of therapy showed 1.13×10^9 , with 68% identified as NE, 23% M, 7% eosinophils and 0% lymphocytes. The eluted M were almost all of CD14^{high} phenotype; with the differential percentage being more than double the average 9% circulating M pool. Of note, two patients underwent SCD treatment with standard heparin HD (SHH), as opposed to RCA. No change in M phenotype was observed, but symptomatic and biochemical adverse events were seen after SHH+SCD treatment, including a greater than doubling of CRP levels. No further studies were undertaken with SHH+SCD treatment due to these adverse events.

Myocardial stunning in ESRD patients undergoing chronic hemodialysis

The mortality rate in ESRD patients requiring chronic hemodialysis treatment is unacceptably high with almost half of the deaths due to cardiovascular disease (CVD). This excessive CVD mortality is not due to classical atherosclerotic disease complications but mainly due to cardiac failure and sudden death, often during the dialysis procedure^{1,2}. The pathogenesis of heart failure in this patient population appears to be due to intradialytic recurrent myocardial stunning (MS) as defined as ischemia mediated transient reduction in myocardial function. Overtime these recurrent ischemic insults results in irreversible fibrotic changes, chronic heart failure, arrhythmias, and sudden cardiac death^{3,30,31}. In this regard, hemodialysis-induced myocardial ischemia and MS has been found to be common in these patients and is significantly associated with high rates of ultrafiltration and intradialytic hypotension⁴. Of note, pediatric patients devoid of atherosclerotic coronary artery disease also have had a high incidence of MS³². MS in HD patients promotes both ischemia induced areas of hypokinesis and akinesis. The majority of these areas of MS improve within 30 minutes post hemodialysis^{33,34}. More frequent HD regimes are associated with lower UF volumes and reduction of intradialytic hypotension and MS events. This relationship may explain in part improved outcomes associated with more frequent HD, such as nocturnal or home HD, compared to the conventional 3 times a week HD treatment program³⁵. MS may be the critical pathophysiologic factor promoting the CV related deaths predominated by heart failure and sudden death in ESRD patients on chronic hemodialysis.

Immunomodulatory Biomimetic Device to Treat Myocardial Stunning in ESRD Patients

This clinical protocol will evaluate the influence of the SCD on myocardial stunning events in ESRD patients in chronic hemodialysis patients. Regional citrate anticoagulation

protocols are routinely used during continuous renal replacement therapy for critically ill patients in intensive care units in many medical centers. A citrate protocol will be adapted for use in this research clinical study in patients with ESRD during one hemodialysis treatment with the added SCD cartridge. We have used this protocol with variations in blood flow/dialysate flow in previous research studies with SCD in both hemodialysis and CRRT treatments. With the currently available citrate intravenous solutions, blood flow through the dialysis system will be 300 mL/min rate. The delivered dose of clearance will be measured online using conductivity dialysance measurements available on Fresenius 2008 T machine. Citrate infusion into the blood will lower the blood ionized calcium level, so that blood ionized calcium levels must be monitored closely. Possible differences may occur in ionized calcium levels in the blood from the extracorporeal circuit obtained at the pre-citrate infusion site compared to the systemic levels may occur. This difference would only occur due to recirculation of blood around the blood access site used for dialysis treatment. Accordingly, assessment of recirculation will be performed using online recirculation module available on Fresenius 2008 T machine. If citrate use results in hypocalcemia this may be associated with paresthesia, tetany, lethargy. If hypocalcemia is not corrected and continues to worsen it may result in severe laryngospasm, seizures, and in rare cases death. Due to these rare potential risks during citrate infusion, ionized calcium levels in the blood from the extracorporeal circuit obtained at the pre-citrate infusion will be carefully monitored, with rapid treatment for protocol subjects in the rare event of developing symptomatic hypocalcemia. Clinical use of regional citrate anticoagulation to prevent circuit clotting (see sections 6.3.4 and 6.3.5) is established and routinely used in clinical hemodialysis at many medical centers. The authors conducted a study of SCD in ESRD patients using citrate anticoagulation at Henry Ford Health System (HFHS) where HFHS IRB deemed the study Non-Significant Risk.

2. Potential Risks and Benefits

The hemodialysis treatment with SCD is comprised of two dialysis cartridges in series within an extracorporeal blood circuit and its associated blood pump systems and blood tubing. The first dialysis cartridge is a conventional high-flux, high surface area Fresenius polysulfone hemofilter (Optiflux 250NR) and the second cartridge is the SCD, which is identical to an FDA approved conventional Fresenius polysulfone F40 filter, Fresenius Medical Care North America, Waltham, MA, U.S.A. approved by the FDA for use in acute and chronic hemodialysis. The extracorporeal perfusion circuit uses standard dialysis arteriovenous blood tubing and is schematized in the Figure 1 with two hemodialysis cartridges in series. The cartridges and blood tubing are placed in a dialysate delivery pump system.

The risks of this device system are similar to risks associated with hemodialysis treatments and include clotting of the perfusion circuit, air entry into the circuit, catheter or blood tubing kinking or disconnection, and temperature dysregulation. The dialysis machines and associated dialysis blood perfusion sets have been designed to identify these problems during treatment with alarm systems and to mitigate any clot or air embolism to the patient with clot filters and air bubble traps. These pump systems and blood tubing sets are FDA approved for this treatment indication.

[figure not shown]

Fig. 1. SCD device.

The blood flow path is changed in the second cartridge compared to conventional use, with blood flowing outside the hollow fibers in the extracapillary space of the hemofiltration cartridge. The lumens of the hollow fibers of the second cartridge will be filled with normal saline, and the entry and exit ports will be capped. This formulation is a reversal of conventional fluid flow mechanics of the dialysis membrane. The risk of this change in flow geometry has proven to be minimal. The use of this second cartridge in this extracorporeal perfusion circuit has been evaluated in over 100 large animals in pre-clinical testing and in 123 patients in Phase I, II, and III clinical studies with no unanticipated adverse events related to the second cartridge and the perfusion circuit. These studies have used both systemic heparin and regional citrate anticoagulation treatments. In fact, in the clinical experience, if clotting occurs within the circuit, it has always been initiated in the first dialysis cartridge. The anticoagulation protocols, both systemic heparin and regional citrate in general (see sections 6.3.4 and 6.3.5), are currently established and routinely used in clinical hemodialysis at many medical centers. Potential benefits may be a short-term improvement of the chronic pro-inflammatory state of ESRD.

For our intended use population the following risk are: cardiac arrhythmias, atrial fibrillation, atrial flutter, bradycardia, sinus tachycardia, ventricular fibrillation, ventricular tachycardia. these risks are all associated with myocardial ischemia. This risk is higher in the intended use population since the enrolled patients will have a tendency to myocardial stunning/ischemia promoting intradialytic hypotension.

3. Study Objectives

The objective of the study is to evaluate the efficacy and safety of SCD in diminishing ischemia induced myocardial stunning events observed in ESRD patients on chronic

hemodialysis requiring aggressive ultrafiltration. Our aim is to decrease myocardial stunning events in hemodialysis patients.

4. Study Design

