8.3.1 Study Treatment

Each Subject will have the treatments described below, during which identical study procedures will be performed during each study treatment.

Treatment 1: Initial standard hemodialysis treatment with heparin (SHH) anticoagulation.

Treatment 2: A single hemodialysis treatment with SCD treatment and regional citrate anticoagulation one week after Treatment 1.

Each subject's safety data will be monitored by the PI on an ongoing basis.

Prior to start of Study Treatment (SHH or SCD Treatment)

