8.3.1.40 Perform 2 D echo

8.3.1.41 Obtain blood for systemic soluble markers according to instructions in **Appendix 2**.

8.3.1.42 Obtain blood for flow cytometry according to instructions in **Appendix 2**.

Before Initiation of SCD Treatment

8.3.1.43 The PI must review all safety data of the Subject and determine their suitability to move to the SCD treatment. Further, the WBC count must be $>4000/\text{mm}^3$, neutrophil count >500 and platelet count $>50,000/\text{mm}^3$ in prior treatments.

Ionized calcium during SCD Treatment

8.3.1.44 The PI may draw more frequent iCa using i-STAT device if deemed necessary for safety concerns.

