Assessment: Echocardiographic parameters which are less (but not entirely) preload and afterload dependent include quantitation of regional wall motion abnormalities as well as calculation of GLS. Normative values for regional wall motion abnormalities are defined as normal thickening and endocardial excursion in all regions and any deviation from normal thickening or excursion is considered abnormal. Regional wall motion will be scored using a standard wall motion scoring scheme. (1=normal; 2=hypokinetic; 3= akinetic; 4=dyskinetic). Scores will be tabulated for each of 16 predefined segments and a global wall motion score calculated as the sum of individual scores divided by the number visualized segments. For this scheme a score of 1 represents normal ventricular function with progressively higher numbers representing progressively worse systolic function. Scores from pre HD, post HD and 24 hour post HD Echos from all 10 patients will be collated and analyzed for statistical significance between Treatment 1 and Treatment 2 groups.

Global longitudinal strain will be obtained using tissue tracking methodology³⁸. There is a significant range within the left ventricle of normal values for regional strain depending on wall location. Values for normal GLS in normal controls have ranged from -16.0 to -22.0. Patients with systemic diseases including hypertension, diabetes and renal disease have all been described to have reduced GLS in the absence of overt systolic dysfunction. As “normal” values for GLS cannot be predicted in the patient population under consideration each patient will serve as his or her own control for tracking improvement or deterioration in global longitudinal strain.

Assessment: The largest body of data regarding using global longitudinal strain for tracking myocardial performance is in the patients receiving cardiotoxic chemotherapeutic agents where a threshold of 10-15% change has been considered as significant variation from baseline³⁹. This will be used as a dichotomous threshold for defining either improvement or deterioration in GLS.

Echocardiographic images will be interpreted at the Echo Laboratory, Frankel Cardiovascular Center, Floor 3. Area B, University of Michigan, Ann Arbor, MI

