8.5 Study Exit Procedures

A Study Termination form will be completed for all patients who have completed the Study Procedures according to the protocol as well as for those who are terminating early for any cause

9. Statistical Considerations

Sample size determination for primary outcome regional wall abnormalities: Our consultant, [name] has previously demonstrated a difference in this variable in 8 to 10 patients using a similar protocol to this proposal when comparing standard and biofeedback dialysis and dialysis cooling ^{33,34}. Sample size of 10 would appear to be sufficient to detect a difference of 20% and is based upon a standard deviation of 14%, significance level of 0.05 and 80% power. In the [name] studies, differences of greater than 20% were observed. We plan to recruit 10 patients in this study, to better ensure an adequate sample size to obtain statistically relevant primary and secondary endpoint comparisons. The patients will serve as their own controls, comparing BL-SHH parameters to SCD therapy parameters. Independent t-test will be used to compare the peak frequency of MS between SHH and SCD sessions. Global LVEF and wall motion in 16 segments in 8 regions at each time point in the dialysis session will be compared using repeated measures and Bonferroni's test for multiple comparisons. IDWG will be compared using paired and unpaired non-parametric testing or t-test if the variable is

normally distributed. These approaches have shown significance in prior studies for MS in HD. Statistical correlations are planned for regional wall abnormalities, inflammatory indices, monocyte subsets and pre-dialysis blood pressures ^{33,34}

10. Adverse Events

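### Subjects withheld from SCD after a safety review can remain in the SHH echo summary, so the two sessions may describe different patients and the contrast may lean toward SCD

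*Combined protocol and SAP*

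**What the plan says.** - **Analysis set.** The Primary Analyses row of the synopsis reads "Descriptive analysis will be conducted on the following parameters in all Subjects exposed to any study hemodialysis treatment". The list below it covers adverse events, regional wall abnormalities and strain, and laboratory and physiological measurements. Having had both sessions is not a condition.
- **Order.** SHH is always Treatment 1. Section 8.3.1 describes Treatment 2 as "A single hemodialysis treatment with SCD treatment and regional citrate anticoagulation one week after Treatment 1".
- **Passage to SCD.** Section 8.3.1.43 states: "The PI must review all safety data of the Subject and determine their suitability to move to the SCD treatment". It adds minimum white cell, neutrophil and platelet counts from prior treatments, but no echocardiographic criterion. The Data Safety Monitoring row of the synopsis agrees: "A safety analysis will be performed on each patient prior to their next hemodialysis treatment by the PI".
- **Comparison.** Sections 8.4.1 and 9 both make each patient his or her own control. Section 8.4.1 also says "Scores from pre HD, post HD and 24 hour post HD Echos from all 10 patients will be collated" and tested between the two treatment groups, which presumes ten patients with both sessions. Section 9 then names an independent t-test for the peak frequency of stunning in SHH versus SCD sessions.
- **Incomplete subjects.** Section 8.5 requires a termination form for completers "as well as for those who are terminating early for any cause". No section says how a subject with SHH only is analyzed, reported or replaced.

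**The concern.** Whether a subject has any SCD result depends on a review of what happened up to and during SHH. Read literally, the SHH column of the primary summary holds everyone treated, and the SCD column holds only those judged suitable to continue.

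For the echo outcomes the link between that review and the result is indirect, but the protocol draws it. Section 1 associates stunning with intradialytic hypotension, and section 2 says of the arrhythmias it lists that "these risks are all associated with myocardial ischemia". Suppose those withheld tend to have the worse SHH echoes, and a patient's stunning is similar from one session to the next. The SHH mean then includes patients whose probably high SCD values are never observed, and SCD looks better with no device effect.

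The own-control wording would prevent this if it were carried into an analysis set. It is not, and an independent t-test does not need pairs. With 10 subjects, one or two such cases are enough to move a mean.

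**Working it through.** **The plan's own figure.** Section 9 gives a difference of 20%, SD 14%, significance level 0.05, power 80% and N = 10. It does not say whether 14% is the SD of one session or of the within-patient difference, nor whether the test is two-sided (two-sided is assumed here).
- Paired t-test, 14 as the per-session SD, correlation 0: SD of the difference = 14 × √2 = 19.8. Power is 81.1% at n = 10 and 75.6% at n = 9, which matches N = 10 at 80%.
- Independent t-test, 10 per session: power 85.5%.
- Paired t-test, 14 as the SD of the difference: power 97.9% at n = 10.

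So N = 10 is reproduced, and this point does not alter it.

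**Inputs for the bias.** From section 9: SD 14, read as the between-patient SD in each session, and 10 patients. Assumed, because the plan gives neither: k = 1 to 3 subjects withheld, and within-patient correlation ρ between sessions from 0 to 0.9. There is no true SCD effect. The scenario withholds exactly the k worst SHH results.

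**Formula.** Let d be the mean of all SHH values minus the mean SHH value of those who proceed. Then d = (k/10) × excess, where excess is the gap between withheld and retained means. For the worst k of 10 normal values the expected excess is about 1.71, 1.587 and 1.522 SD, or 23.9, 22.2 and 21.3 points:
- k = 1: d = 0.1 × 23.9 = 2.4
- k = 2: d = 0.2 × 22.2 = 4.4
- k = 3: d = 0.3 × 21.3 = 6.4

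Those who proceed sit d below average at SHH but, with correlation ρ, only ρ × d below average at SCD. Hence:
- all SHH minus SCD (the stated set) = +ρ × d, an apparent SCD benefit;
- SHH minus SCD in completers only = −(1 − ρ) × d, an apparent SCD harm, which is regression to the mean.

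**Results** (simulation, 40,000 trials per cell, agreeing with the formulas; the completers figures at ρ = 0 are from the formula):

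| ρ | All SHH minus SCD, k = 1 / 2 / 3 | Completers only, k = 1 / 2 / 3 |
|---|---|---|
| 0 | about 0 | −2.4 / −4.4 / −6.4 |
| 0.5 | +1.2 / +2.3 / +3.3 | −1.2 / −2.1 / −3.2 |
| 0.7 | +1.7 / +3.1 / +4.5 | −0.7 / −1.3 / −1.9 |
| 0.9 | +2.2 / +4.0 / +5.7 | −0.2 / −0.5 / −0.7 |

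When the same numbers are withheld at random, both columns are about 0 at every ρ. Against the 20-point design difference, 1.2/20 = 6% and 5.7/20 = 29%.

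**Effect on the tests.** At ρ = 0.5 the independent t-test rejects in 1.2% to 2.6% of null trials, because ignoring the pairing makes it conservative. The paired test on completers rejects in 5.7% to 8.8%, but only 0.7% to 1.4% of trials reject in favor of SCD.

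**Why an all-sessions model helps.** A likelihood-based model in effect estimates the SCD mean as the retained SCD mean plus slope × d. With equal SDs the slope is ρ, so the expected value is −ρ × d + ρ × d = 0 when withholding depends only on the modeled SHH result.

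**The case against.** The selection link is not established. The only numerical criteria in section 8.3.1.43 are blood counts, and a subject stopped for a low count need not have a bad echo. Being prone to intradialytic hypotension is a route into the trial (5.1.8), so hypotension during SHH is not an obvious reason to withhold SCD. Entrants must be able to receive heparin hemodialysis safely (5.1.4), and severe heart failure, ischemic cardiomyopathy and recent acute coronary syndrome are excluded. Nothing in the plan suggests that 2 or 3 of 10 would be withheld. The synopsis also says who is described, not how the sessions are contrasted. The contrast is own-control, and sections 8.4.2 and 8.4.3 already name repeated-measures ANOVA and paired t-tests for markers and cytometry.

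Much of this stands. The bias is conditional and its size is not known from the documents. What does not stand is that the own-control wording settles the matter: section 9 follows it with an unpaired test, and no section defines the set for the contrast.

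A reader might infer more than the documents support:
- *That withheld subjects necessarily worsen the SHH result.* The review covers safety data and counts, not wall motion.
- *That the whole rise in the SHH mean is false benefit.* For example, 3 of 10 withheld at 2 SD worse gives 0.3 × 28 = 8.4 points, or 42% of 20. This needs ρ = 1, and it exceeds the 6.4 points expected even if the three worst results were picked exactly.
- *That the independent t-test produces excess false positives.* In these scenarios it does not go above about 5%.
- *That restricting to completers removes all bias.* It reverses the sign.
- *That the all-exposed set is wrong for adverse events.* It is the usual safety set.

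**Conclusion.** The point holds as a conditional risk to the descriptive SHH versus SCD estimate for wall motion and strain, and as a gap in the analysis sets. If withholding is related to stunning and stunning is correlated between sessions, the stated set gives a false SCD benefit of about 1.2 to 5.7 points for ρ from 0.5 to 0.9. This assumes 1 to 3 of 10 withheld, the worst SHH results selected, and 14 as a between-patient SD. It is near zero if withholding is unrelated to stunning, or if ρ is 0. The planned N and the false-positive rate of the stated test are not harmed. The change is worth making because it is cheap, resolves the conflict between the own-control text and the independent test, and fixes the choice before data are seen.

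**What to change.** In the synopsis and sections 8.4.1 and 9:

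1. Make the SHH versus SCD contrast for echo, strain and markers within-patient: paired differences in subjects who started both sessions. A subject whose SCD was stopped early still counts as SCD. This replaces the independent t-test.
2. Add, as a sensitivity analysis, a likelihood-based repeated-measures model using all observed sessions, because completers-only differences err against SCD by about 0.2 to 3.2 points over the same range.
3. Keep all exposed subjects for adverse events, reported by session with each session's own denominator.
4. List SHH-only subjects individually with their SHH echo values and the reason they did not proceed, and state whether they are replaced.

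No clinical rule changes. The cost is wording, one listing and one extra model, which will be imprecise with at most 10 patients. The paired contrast may lose a few subjects: with 9, 8 or 7 completers, power is 75.6%, 68.9% or 60.9% if the SD of the difference is 19.8, and 96.2%, 93.1% or 88.0% if it is 14. Its conclusions apply to subjects who proceeded to SCD.
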